# 6.3 Intervention

#### 6.3.1 Managed treatments

- 6.3.1.1 Treatment in study.
  - PRO-087

o Active ingredients (lubricant): chondroitin sulfate 0.18%, sodium hyaluronate 0.1%

- o Pharmaceutical form:
- o Prepared by: Sophia Laboratories, S.A. of C.V.
- o Dosage: 1 drop in both eyes, 4 times a day during the waking period
- o Description of the solution: transparent solution, free of visible particles.
- o Description of container: sterile multi-dose bottle

Type of agent	Quantity mg/mL	Function
Chondroitin sulfate	1.8	Active principle (lubricant)
Sodium hyaluronate	1	Active principle (lubricant)
Boric acid	2.00	Active principle
Sodium borate decahydrate	Without showing	Additive
Polysorbate 80	Without showing	Additive
Sorbitol	Without showing	Additive
Potassium chloride	Without showing	Additive
Sodium chloride	Without showing	Additive

#### Table 4. Quali-quantitative formulation of PRO-087

Type of agent		Quantity mg/mL	Function
Magnesium hexahydrate	chloride	Without showing	Additive
Water for the preparation of injectables c.b.p.		1.00	Vehicle

Quali-quantitative formulation of the product under investigation PRO-087. The concentration of the active principles is shown, as well as the substances that act as a buffer additive.

#### 6.3.1.2 Reference treatment

#### - Xyel Ofteno®

- Active principles:
- Pharmaceutical form: Ophthalmic solution
- Prepared by: Sophia Laboratories, S.A. of C.V.
- Dosage: 1 drop in both eyes, 4 times a day during the waking period
- Description of the solution: transparent solution, free of visible particles.
- Description of container: sterile multi-dose bottle

#### Systane Ultra®

- Active ingredients:): Polyethylene glycol 400 0.4%, propylene glycol 0.3%
- Pharmaceutical form: Ophthalmic solution
- Presentation: multi-dose dropper bottle
- Prepared by: Alcon Laboratories, Inc.
- Dosage: 1 drop in both eyes, 4 times a day during the waking period.

#### 6.3.2 Strategies to improve adherence and procedure to monitor adherence

1. Each visit the research subject will return the assigned bottle in order to evaluate the adherence by weight.

- 2. Direct questioning by the IP about the application of the intervention.
- 3. At the IP criteria, messages can be sent or reminder calls can be made.
- 4. Delivery of printed chronogram specifying the date of the visit and its activities
- 5. Journal of the subject.

#### 6.3.2.1 Procedure to monitor adherence

Before delivering the medication to the research subject, the pharmacist must carry out the weighing of the bottles to be delivered. After the return of the medication by the subject will also carry out the weighing. Guidelines to follow for weighing:

- The pharmacist will use the scale provided by the sponsor
- Place the bottle in the center of the scale. You will get the result of the measurement.
- Remove the jar from the balance and put it back in, confirming that the measurement is the same. If it is different, it will weigh one more time and take the average of the 3 measurements
- Record the result in the log and the CRF provided by the sponsor

The adhesion will be calculated considering: the weight of the empty bottle, the weight of the drop, the weight of the bottle with the content, the calculation of the total of drops to be applied during the entire time of intervention and the total weight of the drops applied. The following simplified formula will be used:

$$Ad = \frac{\left(P_i - P_f\right)100}{P_T}$$

Where:

Ad = Adhesion

 $P_i$  = weight of the bottle delivered to the subject at the start

 $P_f$  = weight of the bottle returned by the subject

 $P_T$  = weight of the posology indicated for the intervention

$$P_T = (P_g)G$$

Where:

 $P_g$  = weight of the intervention drop, determined by the research and development department G = number of drops indicated for the intervention

Adherence will be estimated at each visit where the research subject returns the intervention. Only those bottles without apparent physical damage will be considered for the calculation. This result will allow the PI to determine if the subject continues in the study according to the stipulations of the elimination criteria.

The evaluation of the adherence by means of the diary of the subject will be carried out in the following way:

$$Ad = (A_r)100/A_i$$

*Ad* = Adherence

 $A_r$  = Registered applications

 $A_i$  = Applications indicated for the intervention

The final (overall) adhesion will be determined by the average of the adherence of each of the visits.

It will not be considered for the calculation of final adherence if the subject did not return the bottle in two subsequent visits.

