#### Duration of treatment: 10 days

#### Reference product, dose and route of administration, lot:

- 1. **Xyel Ofteno**®. Xantana gum 0.09% / Chondroitin sulfate 0.1% / preservative-free ophthalmic solution. Prepared by Sophia Laboratories, S.A. of C.V., Zapopan, Jalisco, Mexico.
  - a. Dosage: 1 drop 4 times a day during the waking period, both eyes
  - b. Route of administration: topical ophthalmic
- 2. **Systane Ultra®.** Polyethylene glycol 400 0.4%, propylene glycol 0.3%. Prepared by Alcon Laboratories, Inc.
  - a. Dosage: 1 drop 4 times a day during the waking period, both eyes
  - b. Route of administration: topical ophthalmic

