#### 6.2.2.2 Medical and therapeutic criteria

#### 6.2.3 Elimination criteria

- Withdrawal of the consent letter under information.
- Presentation of serious adverse event.
- No tolerability or hypersensitivity to any of the compounds used during the tests (fluorescein, green lysine, tetracaine)
- No tolerability or hypersensitivity to any of the investigational drugs.
- Adherence <50% determined by the diary of the subject or by the weight of the bottle, of the established dose of the pharmacological intervention in any of the visits.

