#### 6.5.1 Procedures to be performed per visit.

#### 6.5.1.1 Scrutiny visit.

- Signature of informed consent: refers to the signing of the written informed consent document. See 10.3 Consent (assent)
- General and ophthalmological clinical history: refers to the technical, clinical and legal document in which the patient's health conditions, medical acts and other procedures performed on the patient are recorded chronologically. It includes the anamnesis and comprehensive ophthalmological exploration that allows to discern the patient's eligibility. If the patient is taken from the established consultation of the study center, he / she will be able to use the existing clinical history, only having to perform an update.
- Taking laboratory samples: see 6.4.3.12 Laboratory tests.
- Pregnancy test: see 6.4.3.11 Pregnancy test.
- Eligibility criteria: refers to the review by the IP, where it states that the subject can be included in the study by meeting the inclusion criteria and not meeting the exclusion criteria. See 6.2 Eligibility criteria
- Intraocular pressure: see 6.4.3.6 Intraocular pressure
- Visual ability: see 6.4.3.1 Visual capacity
- TRL: see 6.4.3.10 Rupture time of the tear film
- Epithelial defects (TF and TVL): see 6.4.3.4.1 Stains
- Eve signs and symptoms: see 6.4.3.4 Eye surface integrity: and 6.4.3.9 Ocular symptomatology
- Subsequent segment; see 6.4.3.7 Subsequent segment
- Vital signs: see 6.4.3.8 Vital signs

6.5.1.2 Basal Visit .

- Review of laboratory tests: refers to the review and analysis by the IP of the results of the BH, QS and PFH. See 6.4.3.12 Laboratory tests.
- Eligibility criteria: with the laboratory results, the subject's profile will be finalized for inclusion or not.
- Assignment: It refers to determining the intervention that the patient will follow during the study. It will be done according to section 7. Methods. Assignment of the intervention. This assignment will be made at the baseline visit (day 0) and will go along with the indication to start the treatment period the next day (day 1).
- Delivery of intervention: Refers to the delivery of the product under investigation to the patient of the study, by the research center. It will be done according to sections 6.3.1 Managed treatments and 6.3.4.1 Delivery and reception.

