- Those subjects who comply with an adherence greater than 60% will be included in the statistical analysis to meet the objective of the study. It was considered that from the minimum dose necessary to obtain a pharmacological effect and the presence of adverse events (exposure) is sufficient to fulfill the general objective of the design, according to the pharmacological characteristics of the product under investigation.

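### The adherence formulas divide each visit's use by the whole-course total, so a perfectly adherent subject scores at most 40% at Visit 1, below the 50% elimination limit

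*Combined protocol and SAP*

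**What the plan says.** Section 6.3.2.1 (Procedure to monitor adherence) gives two formulas.

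- **Bottle weight:** the fall in bottle weight, times 100, divided by P_T. P_T is the weight of one drop times G, the number of drops indicated for the intervention. The text introducing the formula lists what goes into it, including "the calculation of the total of drops to be applied during the entire time of intervention".
- **Diary:** recorded applications, times 100, divided by A_i, the applications indicated for the intervention.

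The same section says: "Adherence will be estimated at each visit where the research subject returns the intervention". It then says: "The final (overall) adhesion will be determined by the average of the adherence of each of the visits".

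Sections 6.3.4.1 and 6.3.4.3 have product dispensed at baseline, Visit 1 and Visit 2 and returned at Visit 1, Visit 2 and the final visit. The schedule in section 6.5 handles the diary in the same way.

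The results feed two limits. Section 6.2.3 eliminates a subject for "Adherence <50% determined by the diary of the subject or by the weight of the bottle", and applies this at any visit. Section 8.3.1 states: "Those subjects who comply with an adherence greater than 60% will be included in the statistical analysis". No section gives a denominator for a single dispensing interval.

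**The concern.** The numerator at each return covers only the product used up to that return. The denominator, as described, covers the whole course. Early in treatment the ratio must therefore be small even for a subject who misses nothing, yet it is compared with limits that make sense only on a scale where full use is 100%.

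Two decisions depend on it: whether a subject stays in the study, and whether the subject enters the main statistical analysis. The partial analysis of the first nine subjects (sections 6.5.2 and 8.3.2) also evaluates adherence. The groups leave little room for error: section 6.6.1 calculates 8 per group and recruits 10, so three subjects wrongly removed from one group leave 7. If sites notice the problem and each picks its own denominator, membership of the analysis will not be consistent.

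A smaller issue sits behind this one. Overall adherence is a plain mean of visit values, although the intervals differ in length.

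**Working it through.** The plan gives no worked adherence figure to reproduce, so the check applies its formula to a subject with perfect use.

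**Inputs**

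- Dose: "1 drop in both eyes, 4 times a day during the waking period" (section 6.3.1), so 1 x 2 x 4 = 8 drops a day.
- Length: "Duration of treatment: 10 days" (Summary), so G = 8 x 10 = 80 drops.
- Dosing starts on day 1, the day after the baseline visit (section 6.5.1.2).
- Visits: days 3, 6 and 11, each with a window of one day either side (section 6.4.4).

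**Formula.** For perfect use, the weight lost equals drop weight times drops used. Drop weight cancels:

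Adherence = 100 x drops used / 80 = 100 x 8d / 80 = 10d %, where d is the number of days of use counted.

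The diary gives the same result: at 4 applications a day, 100 x 4d / 40 = 10d %.

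**Visit 1**

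| Visit 1 on | Visit day counted | Visit day not counted |
|---|---|---|
| day 2 | 20% | 10% |
| day 3 | 30% | 20% |
| day 4 | 40% | 30% |

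Every value is below 50%. Reaching 50% takes 40 drops. Against the 16, 24 or 32 drops due in 2, 3 or 4 days, that is 250%, 167% or 125% of the prescribed use. At Visit 1, interval and cumulative weighing coincide, so this result does not depend on which was meant.

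**Overall value, each bottle weighed for its own interval.** On nominal days, with the visit day counted: 24/80 = 30%, 24/80 = 30%, 32/80 = 40%. Mean = 100/3 = 33.3%. Once all 80 drops are used the three values always sum to 100%, so the mean is 33.3% whatever the visit days. If the final visit is on day 10 and that day's drops are not counted, 9 days are counted and the mean is 90/3 = 30.0%.

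**Overall value, use cumulated from the start.** On nominal days: 30%, 60%, 100%, mean 63.3%. Over the windows:

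- lowest (visits on days 2, 5 and 10, visit days not counted): (10 + 40 + 90)/3 = 46.7%
- highest (Visits 1 and 2 on days 4 and 7, visit days counted, all 80 drops used by the final visit): (40 + 70 + 100)/3 = 70.0%

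**With the drops due in each interval as denominator:** 24/24, 24/24 and 32/32 give 100% at each visit and 100% overall. The drops due must follow actual days. With a fixed nominal 24, a perfect subject seen on day 4 and then day 5, both within window, scores 8/24 = 33% at Visit 2.

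**Plain mean against total use.** Take Visit 1 on day 2 and Visit 2 on day 5, so 16, 24 and 40 drops are due. A subject uses 12, 15 and 20:

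- visit values: 12/16 = 75%, 15/24 = 62.5%, 20/40 = 50%; none is below 50%
- plain mean: 187.5/3 = 62.5%, above 60%
- share of drops used: (12 + 15 + 20)/80 = 47/80 = 58.75%, not above 60%

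**The case against.** The best defence is that the sponsor meant a per-interval denominator. The protocol often uses the word intervention for the product handed over or returned at a visit, and G could be read that way. Section 6.3.4.1 has each supply cover its own period, and the 50% and 60% limits are workable only on that reading. The whole-course phrase stands in a list that also includes the empty-bottle weight, which the simplified formula does not use, so the list does not map one to one onto the formula.

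This is a plausible account of intent, but the text does not carry it. The only phrase that fixes the time span of the drop count names the entire intervention, and no section says otherwise.

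The formula also takes the starting weight of the bottle given at the start, which could suggest cumulative weighing. Staged dispensing and return make that less likely. It changes the overall figure but not the Visit 1 failure.

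Section 6.3.2.1 says the result allows the investigator to determine whether the subject continues, so sites might not act on an impossible figure. That lessens the practical risk, but relies on sites departing from the rule.

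A reader might also infer that plain averaging can badly inflate overall adherence, for instance for a subject with full use in two intervals and none in the third. The 50% rule at any visit would already catch that subject. With at least 50% at every visit and nominal intervals, the plain mean exceeds the share of drops used by at most 3.3 points (100%, 100% and 50%: mean 83.3%, against 64/80 = 80%). Visit windows can widen this somewhat. The averaging point is a refinement only.

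**Conclusion.** The point stands: wrong as written. With a whole-course denominator of 80 drops, a perfectly adherent subject scores 20-40% at Visit 1 (10-30% if the visit day is not counted) and so meets the 50% elimination criterion, on either weighing reading. The diary offers no way out, because its denominator is worded alike and section 6.2.3 accepts either measure.

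The overall figure is conditional. It is about 33% (30% in the one window case shown) with interval weighing, which is below 60%, and about 47-70% with cumulative weighing, which may fall on either side.

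A reader might infer that the trial would be left with nothing to analyse. The documents do not support that. Section 8.3.1 reports adverse events for all eyes of randomised participants whatever their adherence, and section 8.3.3 describes a population defined by visits completed. What is at risk is continuation in the study and membership of the analysis restricted to adherence above 60%.

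The result rests on the stated dose, duration and visit windows, and on reading G and A_i as whole-course totals. It needs no outside figure.

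**What to change.** In section 6.3.2.1:

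1. Define G as the drops due, and A_i as the applications due, over the actual days between dispensing and return of that bottle or diary. State whether the visit day counts. Reconcile the sentence about the entire time of intervention with this definition, and say that the starting weight is that of the bottle being returned.
2. Define overall adherence as total used divided by total due over all intervals, in place of the plain mean of visit values.

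Check the revised definitions against the limits in sections 6.2.3 and 8.3.1. The limits themselves are for the sponsor to set.

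The cost is about two sentences and a change to the CRF calculation. No new data are needed, since dispensing and return weights and diary entries are already collected at each visit.

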# 6.3.3 Treatments and concomitant interventions allowed and prohibited during the study.

The use of concomitant medications by any route of administration during the intervention period will not be allowed. Except those specified for the study procedures. The objective of this restriction is to avoid pharmacological interactions that could alter the results of the evaluated variables.

# 6.3.4 Treatment management.

The interventions will be provided by Sophia Laboratories, S.A. of C.V., for each research center. They will be labeled, reconciled and weighed previously. The handling of the treatment will be under the responsibility of the researcher or a designated member of his team.

#### 6.3.4.1 Delivery and reception.

Delivery will be made in closed cardboard boxes by means of a courier service or directly by the sponsor's staff to the home of the research center according to the study plan.

The reception will be exclusively carried out by the research center team, including the researcher. You must check the good condition of the primary packaging (box). In the event that it shows alterations or defects in its integrity that from its judgment could have damaged the content, it should report it to the sponsor. If the package does not show significant defects, it will proceed to open it.

Inside you must locate the acknowledgment document and the logger (data logger) of temperature and humidity. You should check that the registered temperature and humidity comply with the specifications for transport and shelter (see section 6.3.4.2 Storage). Verify the content (interventions) with what is reported in the document. In case the document corresponds to the content, it will sign the receipt and send it to the sponsor. Otherwise, notify the sponsor.

In the study center, the personnel assigned by the PI will deliver the corresponding treatment to the subjects admitted, sufficient for the period to be covered. The delivery will be made in stages, medication will be delivered at the baseline visit, on visits 1 and 2. The center must register the medication delivered.

#### 6.3.4.2 Storage.

The medication must be stored in a secure area with restricted access.

The storage temperature should be <30 ° Celsius.

The research center has the obligation to record, in the format designated by the sponsor, the temperature and humidity registered in the data logger. This record should include the current temperature and humidity, as well as the minimum and maximum of each of these. It must be done at least once a day, on business days.

Said data will be compared by the clinical monitor according to the registration in the data logger.

#### 6.3.4.3 Return.

The research subjects will return to the personnel indicated by the IP in the center their treatments in visits 1, 2 and final. The refund will be made by the research center when the sponsor indicates it. Prior to the return the research center must make a count of the assigned medication and the remaining medication, with the aim of creating an inventory which serves for the final filling of the medication return form.

#### 6.4 Outcome variables.

#### 6.4.1 Security variables.

#### 6.4.1.1 Primary outcome variables.

- Density of goblet cells
- Presence of adverse events.
- Intraocular pressure.
- Visual ability
- Laboratory tests: BHc, QS and PFH.
- Epithelial defects in cornea and conjunctiva.
- Ophthalmological signs: conjunctival hyperemia, chemosis.

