# 6.2 Eligibility criteria

# 6.2.1 Inclusion criteria

- Signed informed consent.
- Systemically and ophthalmologically healthy subjects evaluated during the clinical history.
- Age between 18 to 40 years.
- Both genders.
- Blood tests [complete blood count (BHc), three-element blood chemistry (QS) and liver function tests (PFH)] within normal parameters specified by the reference laboratory with a lower and upper margin of 10%.

- Vital signs within normal parameters.
- Visual ability 20/30 or better, in both eyes.
- Intraocular pressure ≥11 and ≤ 21 mmHg.

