#### 6.4.3 Methods and scales to be used for the measurement of the variables

Variable	Unity	Symbol	Туре	Method of measurement	Normal value
Age	Years		Continuous	Calculation from the date of birth	NA
Gender	Female Male	F / M	Nominal	Direct questioning	NA
Adverse events	Number of cases	n	Discreet	Count	NA
Intraocular pressure	Milimeters of mercury	mmHg	Continuous	Goldman's applanation tonometry	11 - 21
Visual ability	Fraction	Snellen	Nominal	Primer	
Tear rupture time	Seconds	S	Continuous	Direct count	> 10
Eye comfort index	points		Discreet	Questionnaire	
Adverse events	Present / Absent		Nominal	Comprehensive valuation	Absent
Goblet cell density	Cells per square millimeter	Cel/mm 	Continuous	Cytology by impression	> 500 cel/mm 
Vital signs					
Heart rate	Beats per minute	lpm	Discreet	Auscultation	60 - 100
Breathing frequency	Breaths per minute	rpm	Discreet	Auscultation	12 – 24
Systemic blood pressure	Milimeters of mercury	mmHg	Continuous	Non-invasive auscultatory measurement	< 120 / 80
Previous segment					
Epithelial defects	Degrees		Discreet	Direct observation with fluorescein and green lysamin stain	Oxford Scale

Sophia Laboratories, S.A. of C.V.

Variable	Unity	Symbol	Туре	Method of measurement	Normal value
Ophthalmologic signs ar	nd symptoms				
Conjunctival hyperemia	Normal / Very Light / Mild / Moderate / Severe		Ordinal	Direct observation. Classification of Efron.	Normal
Chemosis	Present / Absent		Nominal	Direct observation	Absent
Burning	Severity: Absent, very mild, mild, moderate and severe		Nominal	Direct questioning	Absent
Foreign body sensation	Severity: Absent, very mild, mild, moderate and severe		Nominal	Direct questioning	Absent
Pruritus	Frequency: At all times, almost at all times, 50% of the time, almost in no time, at any time		Nominal	Direct questioning	Absent
Postinstilation symptoms	5				
Burning	Present / Absent		Nominal	Journal of the subject	Absent
Foreign body sensation	Present / Absent		Nominal	Journal of the subject	Absent
Pruritus	Present / Absent		Nominal	Journal of the subject	Absent
Red eye (symptom)	Present / Away		Nominal	Journal of the subject	Absent

Sophia Laboratories, S.A. of C.V.

Variable	Unity	Symbol	Туре	Method of measurement	Normal value
Posterior segment					
Magula	Normal /				
Macula	Abnormal		Nominal	Observación directa	Normal
Optical disk integrity	Normal / Abnormal		Nominal	Observación directa	Normal
Blood count					
Erythrocytes		M/uL	Continuous		

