Hemoglobin	Grams over deciliter	g/dL	Continuous		
Hematocrit	Percentage	%	Continuous		
VGM	Femto liters	fL	Continuous		
НСМ	picograms	pg	Continuous		
CMHbG	Grams over deciliter	g/dL	Continuous		
Leukocytes	Thousands per liter units	Mil/uL	Continuous		
Platelets	Thousands per liter units	Mil/uL	Continuous		
Myelocytes	Percentage	%	Discreet		
Metamyelocytes	Percentage	%	Discreet		
Bands	Percentage	%	Discreet		
Segmented	Percentage	%	Discreet		
Lymphocytes	Percentage	%	Discreet		
Monocytes	Percentage	%	Discreet		
Eosinophils	Percentage	%	Discreet		
Basophils	Percentage	%	Discreet		
Blastos	Percentage	%	Discreet		
Blood chemistry					
Glucose	Milligrams on deciliter	mg/dL	Continuous		
Urea	Milligrams on deciliter	mg/dL	Continuous		
Creatinine	Milligrams on deciliter	mg/dL	Continuous		
Liver function tests					

Variable	Unity	Symbol	Туре	Method of measurement	Normal value
Alanine transferase	Units on liter	U/L	Continuous		
Aspartate transferase	Units on liter	U/L	Continuous		
Total bilirubin	Milligrams on deciliter	mg/dL	Continuous		
Direct bilirubin	Milligrams on deciliter	mg/dL	Continuous		
Indirect Bilirubin	Milligrams on deciliter	mg/dL	Continuous		

Table 5. Scales to be used.

The following describes the methods and scales that will be used for the measurement of the variables, which are in strict alphabetical order:

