#### 6.4.3.12 Lab tests.

The PI will deliver to the subject the order of the studies of BH, QS and PFH, to be carried out in the clinical laboratory designated by the sponsor. The clinical laboratory will deliver to the IP the results for its assessment and registration. The normal parameters to be considered will be the ranges established by the laboratory, Nevertheless the clinical criterion of the PI will prevail in the decision of normality or abnormality of the results.

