# 8.3 Statistical methodology

#### 8.3.1 Analysis of primary and secondary outcome variables.

The statistical analysis will be carried out by personnel from Sophia Laboratories, S.A. of C.V The statistical program SPSS version 19 (IBM Corporation, Armonk, NY, USA) will be used.

The designated personnel will be blinded to the intervention groups. The coding will be done using consecutive numbers for each intervention group.

The data will be collected and sorted in an excel sheet. Later they will be exported to the platform of the SPSS program. The variables will be categorized according to their nature.

CONFIDENTIAL

The result of the continuous quantitative variables will be presented in measures of central tendency: media, standard deviation and ranges. **See Table 5**. Scales to be used

The normal distribution of the results will be obtained by the Kolmogorov-Smirnov test.

The statistical analysis of the continuous **quantitative variables** to find significant differences (p) will be the following:

- Intra-group analysis: Wilcoxon rank test.
- Inter-group analysis: Kruskal-Wallis test.

The level of difference to consider significance will be an alpha of 0.05 or less.

The result of nominal and ordinal qualitative variables will be presented in frequencies, proportions and percentages. See table 1 (section 6.4.3).

The statistical analysis to identify significant differences of the **qualitative variables** will be done by creating 2x2 contingency tables and will be done as follows:

- • Intra-group difference: McNemar test.
- • Difference between groups: χ2 test (Chi-square) of Pearson.
- The level of difference to consider significance will be of an alpha of 0.05 or less.
- For the reporting of adverse events all eyes of those participants who were randomly assigned to an intervention group after the baseline visit will be considered. The results will be expressed in number of cases (eyes).
- The final report of the results will be shown in tables or graphs, as appropriate.
- It will be considered that the investigational drug is safe and tolerable when there are no clinical and statistical differences in all the variables of primary outcome, with respect to its comparators.

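### The laboratory part of the primary safety rule is 25 undirected, unadjusted analyte comparisons with no criterion for a clinical difference between arms: identical arms would show at least one difference in roughly 40-70% of trials

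*Combined protocol and SAP*

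**What the plan says.** Section 6.4.1.1 puts "Laboratory tests: BHc, QS and PFH" in the list of primary safety variables as a single line. Table 5 (section 6.4.3) then sets out the panel as individual rows, from "Erythrocytes" to "Indirect Bilirubin", each with a type and, for nearly all, a unit. There is no composite and no stated direction of harm. The normal-value cells are blank for these rows, but section 6.4.3.12 supplies the normal limits by reference to the clinical laboratory's ranges and adds: "Nevertheless the clinical criterion of the PI will prevail in the decision of normality or abnormality of the results".

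For continuous quantitative variables, section 8.3.1 specifies "Inter-group analysis: Kruskal-Wallis test" and "The level of difference to consider significance will be an alpha of 0.05 or less". It gives no multiplicity adjustment. The synopsis assigns the same test to quantitative variables without restricting it to continuous ones. Section 8.3.1 closes with the decision rule: the product is safe and tolerable when "there are no clinical and statistical differences in all the variables of primary outcome, with respect to its comparators".

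Samples are taken at screening and at the final visit (section 6.5), and the final results are reviewed at the safety call.

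**The concern.** The rule treats any difference from the comparators as evidence against safety, and the laboratory line alone supplies up to 25 opportunities for one. Kruskal-Wallis has no direction. A favourable shift, a shift wholly inside the reference range, or a gap between the two comparators that does not involve PRO-087 can each produce a significant result. Entry values must lie within the laboratory's limits allowing a 10% margin (section 6.2.1), and sections 5.3.1.1 and 5.3.2.1 report no corneal absorption of either active ingredient. Most between-arm laboratory differences are therefore likely to be noise.

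What laboratory safety monitoring looks for is a new, clinically important abnormality in an individual. A rank comparison of three groups of 10 is poorly suited to finding that. At stake is whether the laboratory component of the study's single conclusion reflects harm or chance.

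**Working it through.** The plan states no error rate for the set of laboratory comparisons, so there is no figure of its own to reproduce.

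**Inputs from the documents**
- Blood count rows in Table 5: 17 (8 typed continuous, 9 differential percentages typed discrete).
- Chemistry rows: 3. Liver rows: 5. All 8 are typed continuous.
- Total: 17 + 3 + 5 = 25. Typed continuous: 8 + 3 + 5 = 16.
- Alpha 0.05 per test; three arms of 10 (section 6.6.1), or 8 after the planned losses.

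**Step 1: independent tests, no true difference.** P(at least one) = 1 − 0.95^k.
- k = 25: 1 − 0.95^25 = 0.723
- k = 16: 1 − 0.95^16 = 0.560
- k = 10: 1 − 0.95^10 = 0.401

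One half is passed at k = ln 0.5 / ln 0.95 ≈ 13.5. Kruskal-Wallis with 10 per arm has a true size of about 0.046, so simulation gives about 0.69-0.70 for 25 independent analytes and 0.53 for 16.

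**Step 2: correlated analytes.** The analytes are plainly dependent, and the documents give no correlations, so these panels are assumptions. Red-cell indices were derived from one another, the differential was made to sum to 100%, total bilirubin was direct plus indirect, ALT and AST were correlated, and myelocytes, metamyelocytes and blasts were constant at zero. Each figure is from 20,000 simulated null trials.

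| Rows tested | Dependence assumed | P(at least one p ≤ 0.05) |
|---|---|---|
| All 25 | independent | about 0.70 |
| All 25 | block correlation, moderate to strong | 0.53-0.58 |
| All 25 | uniform r = 0.5 | 0.48 |
| 16 continuous | block correlation | 0.42-0.46 |
| Any set worth 10 independent tests | – | 0.40 |

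In the moderate-correlation panels, 8 per arm instead of 10, or change instead of final value, moves the all-rows figure only between 0.57 and 0.58. The expected number of false differences there is about 22 × 0.046 = 1.0 per trial. A uniform r of 0.7 across all 25 would give 0.34, but that would require blood count, glucose and bilirubin to move together, which I regard as extreme.

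**Step 3: one marked rise in one subject.** With N = 30 the rank sums total 465, or 155 per arm when balanced. Suppose one PRO-087 subject moves to the top rank, lifting that arm's sum by about 15 and lowering the others by about 7.5 each. Then

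H = 12/(30 × 31) × (170² + 147.5² + 147.5²)/10 − 3 × 31 = 93.44 − 93 = 0.44,

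against a critical value of 5.99 (p ≈ 0.80). By simulation, with an assumed lognormal ALT (median about 22 U/L, log-SD 0.35), the test rejects in 4.4% of null trials, 4.4% with one PRO-087 subject set to 400 U/L, and 6.9% with two.

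**The case against.** Five points have force.

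- **The rule says clinical and statistical.** A reader might infer that any chance p-value fails PRO-087. The text does not establish this: on the joint reading, a significant but clinically empty difference would not count. What remains is that no criterion for a clinical difference between arms is written down, and the investigator's normality judgement in section 6.4.3.12 is not connected to the rule.
- **More than half is not secure.** It needs all 25 rows, as the synopsis wording allows, and moderate correlation. Section 8.3.1 speaks of continuous variables. On that reading 16 rows remain and the correlated figure falls below one half. However, section 8.3.1 names no other test for the discrete quantitative rows.
- **Separate testing is inferred.** The plan never says outright that each analyte is tested, and section 8.3.1 cites Table 5 for presentation. But no other laboratory variable is defined, so there is nothing else to test.
- **A marked liver-enzyme rise would not go unnoticed.** A reader might infer that from Step 3. The investigator reviews every result, the safety call covers the final samples, ranges are reported, and adverse events are themselves a primary variable. The narrower point stands: such a rise would not register through the laboratory comparison.
- **Normal limits are not missing.** They are set by reference to the laboratory. What is absent is their use in the analysis.

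**Conclusion.** The concern holds in a bounded form. If each analyte is tested, identical arms would yield at least one laboratory difference in roughly 40-70% of trials. The position in that range depends on whether the nine discrete rows are included and on correlations that must be assumed. Even the lower end is too high for one line among several primary variables.

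The rule works badly on either reading. If a statistical difference alone counts, noise can deny the safety conclusion. If both a clinical and a statistical difference are needed, the clinical part is decided after the results are seen, and an important change in a single subject cannot count because the rank test will not be significant. This is more than missing detail, and the plan should be changed. It does not show that subjects are unprotected during the study.

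**What to change.** In sections 6.4.1.1 and 8.3.1, define the laboratory variable in the safety rule per subject: at least one new value at the final visit outside the laboratory's reference range that the blinded investigator judges clinically significant (yes/no). Define new against that subject's screening value, since section 6.2.1 admits values up to 10% beyond the limits. Report counts by arm, list every case, and treat only an excess on PRO-087 as evidence against it. Present the 25 analytes descriptively as change from screening, outside the decision rule.

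The data are already collected, and section 6.4.3.12 already provides for the judgement. The costs are a protocol amendment with committee review and regulatory authorisation (section 10.2), partial overlap with the adverse event outcome, and a move away from the undirected similarity hypothesis of section 5.5.3 for this variable. With 10 subjects per arm, a yes/no comparison has little power and is less sensitive to small mean shifts. The case listings and descriptive tables are therefore an essential part of the change.
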